Assess efficacy of the multilevel interventions (hypothesis testing). Cluster randomization study design and interventions. We propose a cluster randomized study implemented in the six selected geographic zones in Lusaka, each served by a government-operated clinic providing HIV and cervical cancer screening services. Zones, with their respective clinics, will be randomized into three groups (zones with IWC clinics and SHIELD intervention, zones with only SHIELD intervention, and control zones with no IWC clinic or SHIELD interventions. AGYW in the control zones will be offered one education session on HIV prevention and treatment) to assess the impact of offering IWC clinics coupled with the SHIELD intervention compared to the standard of care (see Exhibit 1 above). The study team will also evaluate whether a similar impact can be achieved with control clinics when the SHIELD intervention is offered in the community. The SHIELD intervention, as described in Section 3.2, will begin with training sessions for AGYW and their families. This will be followed by PN-facilitated youth clubs that will meet about once a month during the 12-month study timeframe. Two-four PNs will be assigned to each clinic zone with the SHIELD intervention, and one-two PN each will be assigned to the two control clinic zones to assist with data collection and follow-up activities. The PNs in zones with the IWC clinics will also serve as community liaisons to support clinic-community linkages. The health centers in which the **primary endpoint for the HIV/u cohort** is the proportion with any HIV testing at 12 months. **For the HIV+ cohort, we plan to assess the primary endpoint:** viral load suppression, measured as proportion with undetectable viral load at 12 months. The secondary endpoints are the proportion with decrease in HIV risk behavior, repeat HIV testing (each 6-month period), HIV infections diagnosed through voluntary HCT, linkages to HIV care, and adherence to ART. We will also conduct a targeted 6-month post-intervention data collection after the end of the 12-month intervention period. See **Exhibit 4** for endpoint definitions and biological, self-report, and clinic audit measures collected at 6- and 12-month follow up. To assess the impact of the SHIELD intervention on the mediating outcomes, the study team will collect data from AGYWs across all six clinic zones at baseline and at 6- and 12- month follow-up. The study team will also track health care service use by conducting clinic audits at all six clinic sites. We plan to retain the intervention cohort for a maximum of 24 months total to allow for initiation of the intervention and follow-up activities (12 months of intervention and follow-up after intervention completion).

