Hypotheses on intervention effect. The study team will test the following hypotheses: (1) HIV-/u AGYW from zones with IWC clinics and who receive SHIELD intervention will have higher HIV testing than AGYW in zones without the IWC clinics (including those receiving SHIELD intervention with usual care clinics); (2a) HIV+ AGYW from zones with IWC clinics and who receive SHIELD intervention will have higher viral load suppression (2b) than AGYW in zones without the IWC clinics (including those receiving SHIELD intervention with usual care clinics); (3) HIV+ AGYW from zones with IWC clinics will receive more-timely linkages to care than AGYW in zones without a IWC clinic; (4) AGYW from zones who receive SHIELD intervention will have improved self-efficacy (4a) and social support (4b), and reduced HIV risk behaviors (4c) compared to AGYW from zones not receiving the intervention.

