Cost-effectiveness, budget impact, and policy implications. The study team will use a previously validated instrument, The Cost Assessment Tool,⁶⁰ to create a tailored data collection approach to collect resource use information on the interventions. Our main goal is to estimate the implementation cost of the IWC and the SHIELD interventions from the program perspective (which will reflect MOH resources needed to sustain interventions), but the study team will also derive the start-up costs related to developing the interventions to inform future adaption of these interventions to other settings. The study team will estimate labor hours of IWC clinic staff, PN, and other staff by prospectively tracking time spent by each project staff member implementing the intervention on a pre-defined set of activities and use hourly wage to calculate cost. The study team will also document the expenditure on non-labor resources. Using standard economics methodology,^{61,62} the study team will explore economies of scale that can be achieved during scale-up. The cost information, along with the effectiveness impact of the IWC and SHIELD interventions, will be used as inputs in previously validated models and approaches developed by RTI.⁶³ The study team will evaluate the tradeoff, or return on investment, between investing in HIV prevention and lowering HIV treatment cost over the long term. The usual care (base case) will be compared to the long-term effectiveness of including the IWC clinic-based intervention with and without the SHIELD community-based interventions to address barriers along the continuum of care. The study team will report the projected decrease in HIV incidence,

increase in community-level viral load suppression, and incremental cost per quality-adjusted life years. The study team will conduct policy simulations to assess the impact of scaling up the interventions to the population level; perform sensitivity analysis, varying the range of effectiveness and cost estimates; and generate potential best- and worst-case scenarios. The study team will create tornado and spider diagrams to display this uncertainty assessments graphically to policy makers. This cost-effectiveness analysis will be complemented by a budget analysis, which will identify the financial outlays that will be required annually to implement the intervention during the implementation trial in the scale-up process.

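### The economic plan omits the randomised SHIELD-only strategy, lists an IWC-only strategy with no trial arm, and specifies no cost-per-QALY comparison of IWC+SHIELD with SHIELD alone

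*Combined protocol and SAP*

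**What the plan says.** The randomised groups are set out in Section 3.3, Research Protocol: "zones with IWC clinics and SHIELD intervention, zones with only SHIELD intervention, and control zones with no IWC clinic or SHIELD interventions". The same paragraph gives the SHIELD-only group its own question: "The study team will also evaluate whether a similar impact can be achieved with control clinics when the SHIELD intervention is offered in the community". Hypotheses 1 and 2 set IWC+SHIELD zones against zones without an IWC clinic, "including those receiving SHIELD intervention with usual care clinics".

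The economic plan is the paragraph on cost-effectiveness, budget impact and policy implications in the same section. Its comparison sentence reads "The usual care (base case) will be compared to the long-term effectiveness of including the IWC clinic-based intervention" and continues "with and without the SHIELD community-based interventions to address barriers along the continuum of care". The outputs listed next include "increase in community-level viral load suppression, and incremental cost per quality-adjusted life years". The paragraph does not say what the ratio is incremental to. It gives no rule for ordering strategies or removing dominated ones. Both IWC and SHIELD are to be costed, and the sensitivity analysis varies effectiveness and cost but mentions no change of comparator.

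**The concern.** For the Ministry of Health, the three randomised groups are mutually exclusive options: continue usual care, add SHIELD, or add SHIELD and IWC clinics. With more than two such options, the ratio that informs each step compares an option with the next less costly option that is not dominated. For IWC clinics, if SHIELD alone is cheaper and not dominated, that is IWC+SHIELD against SHIELD alone.

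The economic paragraph does not provide this comparison. Its strategies, read literally, are usual care, IWC without SHIELD and IWC with SHIELD. The trial observes the first and the third. It does not observe IWC without SHIELD, so that effect would need a modelling assumption, for example that the two components add. SHIELD alone, which the trial does observe, is missing.

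Cost-effectiveness is Objective 3, and its results go to government at the planned policy forum. A package ratio against usual care could be taken as the value of IWC clinics when it mixes two components that may differ in value.

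**Working it through.** **Plan's own figure.** There is none to reproduce. The documents give no cost, QALY, cost-effectiveness ratio or willingness-to-pay threshold. All costs and SHIELD-only effects below are assumptions.

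**Strategies side by side** (both sources are in Section 3.3)

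| Strategy | Randomised group | Named in the economic paragraph |
|---|---|---|
| Usual care | yes | yes, as base case |
| SHIELD only | yes | no |
| IWC+SHIELD | yes | yes |
| IWC only | no | yes |

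Suppose the economic list were analysed stepwise. If IWC alone were the cheaper of its two active strategies, the second step would be IWC+SHIELD against IWC alone. That is the value of adding SHIELD. The value of adding IWC to SHIELD cannot be obtained from that list.

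**Why the package ratio is not a substitute.** Let SHIELD cost cS with effect e, and let the package cost cS + cI with effect E, all relative to usual care.

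- Package v usual care: P = (cS + cI)/E
- SHIELD v usual care: S = cS/e
- IWC step (package v SHIELD): I = cI/(E − e)
- With w = e/E, P = w·S + (1 − w)·I

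So P lies between S and I. If S is below P, then I is above it. If S is above P, then I is below it.

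**Illustration in cost per percentage point.** E = 15 points. This is the detectable improvement in the sample-size paragraph, used only as a convenient scale. It is not a predicted package effect. Equal costs are assumed, cS = cI = 1, so P = 2/15 = 0.133.

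| SHIELD-only effect e | I = 1/(15 − e) | I/P |
|---|---|---|
| 5 | 1/10 = 0.10 | 0.75 |
| 7.5 | 1/7.5 = 0.133 | 1.0 |
| 10 | 1/5 = 0.20 | 1.5 |
| 12 | 1/3 = 0.333 | 2.5 |
| 14 | 1/1 = 1.00 | 7.5 |

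Check of the identity at e = 10: w = 10/15, S = 1/10 and I = 1/5, so P = (10/15)(0.10) + (5/15)(0.20) = 0.067 + 0.067 = 0.133.

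**Sensitivity to the cost assumption.** If IWC costs twice SHIELD (cS = 1, cI = 2), then P = 3/15 = 0.20 and I/P = [2/(15 − e)]/0.20 = 10/(15 − e). At e = 5, 10, 12 and 14 this gives 1.0, 2.0, 3.3 and 10. The break-even effect is 15·cS/(cS + cI): 7.5 points with equal costs and 5 points here.

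**Illustration in QALYs (assumed values).** SHIELD costs 40 for 0.10 QALY, which is 400 per QALY. The package costs 90 for 0.12 QALY, which is 750 per QALY against usual care. The IWC step is (90 − 40)/(0.12 − 0.10) = 50/0.02 = 2,500 per QALY. Any threshold between 750 and 2,500 would accept the package on the usual-care ratio and reject the IWC step.

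**The case against.** The strongest reply is that the plan does not forbid the right analysis. A reader might infer that cost per QALY is restricted to a comparison with usual care. The text does not say so. The sentence naming usual care concerns long-term effectiveness, the cost-per-QALY ratio has no stated comparator, and a base case is a reference point that leaves stepwise increments open. The paragraph also relies on existing validated models whose conventions cannot be seen here. All of that stands. It does not repair the strategy list, however. A stepwise analysis of the strategies as named still has no SHIELD-only option.

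A second reply is that the trial would not conceal a strong SHIELD-only result. This also stands. Hypotheses 1 and 2 include SHIELD-only zones in the comparison, the primary analysis examines all three groups, and both components are costed. A reader might infer that the plan would lead to scale-up of IWC clinics against the trial's own data. That would require the effectiveness results to be ignored, and the documents do not support it. Those hypotheses concern effects only, though, and do not supply a cost-per-QALY increment.

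A third reply is that the direction of error is unknown. It stands in full. Showing only SHIELD-only effects of 10 points or more would suggest that the usual-care ratio always flatters IWC. With equal costs it does the reverse below 7.5 points. The illustrations also leave out the treatment-cost savings that the plan intends to weigh, and the first is in percentage points, so its factors carry over to QALYs only if QALY gains are proportional to those points.

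**Conclusion.** The concern holds in this form. The economic paragraph names usual care and no other comparator, leaves out the randomised SHIELD-only strategy, includes an IWC-only strategy without a trial arm, and specifies no cost-per-QALY comparison of IWC+SHIELD with SHIELD. Followed as written, it cannot give the ratio for adding IWC to SHIELD. This rests on the text alone.

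The size is illustrative. On assumed equal costs and a 15-point package effect, the IWC-step ratio runs from 0.75 to 7.5 times the usual-care ratio as the SHIELD-only effect goes from 5 to 14 points. Which side of 1 applies in this trial cannot be known from the documents. It is therefore not established that the plan makes IWC look good value when it is not, only that the planned ratio could mislead either way. The point affects Objective 3 and leaves the primary endpoint analyses untouched. It should be corrected before the economic results are reported.

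**What to change.** Replace the comparison sentence in the cost-effectiveness paragraph so that:

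- the strategies are the three randomised groups: usual care, SHIELD only and IWC+SHIELD;
- they are ordered by cost, and dominated and extendedly dominated options are removed;
- each ratio is reported against the next less costly non-dominated option, with its uncertainty, and the IWC+SHIELD v SHIELD comparison is shown explicitly;
- ratios against usual care are kept as supplementary;
- any IWC-only result is labelled as model-based, with its assumption (for example, additivity) stated.

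The budget analysis should use the same increments. The cost is a change of wording and one extra table from the same model runs. No new data are needed, because SHIELD-only outcomes come from a randomised group and both interventions are already to be costed.

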3.2 Overview of the interventions

SHIELD intervention. The SHIELD intervention is based on social cognitive theory, which posits that positive behavior change requires knowledge and skills to increase behavioral capability, development of self-efficacy to increase the belief that one can achieve the desired outcomes, and social support to provide positive reinforcement and develop positive outcomes expectations.⁴⁶ We developed a modular program for AGYW that increases knowledge, skills, and self-efficacy to engage along the HIV prevention and care continuum, and a program for family members (up to four participants in addition to the AGYW; 10 years and older) to increase social support. To reflect AGYW's evolving cognitive and decisional capacity, judgement, emotional development, risk, and health-seeking behaviors, intervention content for both AGYW and families were tailored for five distinct groups to reflect development stage and

AGYW's HIV status. Content areas were adapted from existing evidence-based interventions, such as Stepping Stones^{30,31} and Families Matter!^{47,48} based on CAB and YAB input and formative research with AGYW, caregivers, and community leaders. Modules address HIV prevention and treatment, general wellness and SRH, approaches to combat stigma and discrimination, and skills for better communication, and include new content on health service availability and access to increase self-efficacy in seeking health care services. SHIELD educational materials were pre-tested. The SHIELD sessions will be offered to AGYW and their families in the 4 communities randomly assigned to intervention arms. The AGYW in the usual care arm will receive one education session focused on stigma and HIV care. SHIELD education session content is presented in **Exhibit 1** for the AGYW sessions and **Exhibit 2** for the family sessions. We have noted content that will be included in core sessions along with content that will be included in the basic education provided to the control group participants. The core sessions will be provided to all participants in the intervention communities while all other sessions will be optional content for future meetings within the intervention communities.

Exhibit 1. SHIELD Content Areas for Adolescent Girls and Young Women Program

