| AGYW and Families | 
 1. What you see in me (All) 2. Making puberty easier (parents of AGYW ages 10-12) 3. HIV, AIDS and STIs- Myth or Fact (All)* 4. Helping children express their feelings (ages 10-12) 5. Taking responsibility for pregnancy: Community responsibility (ages 13-24)* | 
 1. Non-verbal communication (All) 2. Sharing information with family members: challenges and possibilities (HIV+ ages 16-24)* 3. Providing emotional support after a child learns that you or they are HIV positive (All) 4. Analyzing stigma against AGYW (All)* |

* Indicates core topic area

IWC Clinic

The Integrated Wellness Care (IWC) clinic for AGYW will be established in 2 randomly selected health centers participating in this study communities. The clinic will provide integrated HIV and sexual and reproductive health services to both participating HIV-/u and HIV+ AGYW facilitated by a trained nurse. Specifically, the IWC clinic will offer:

- HPV vaccination
- HIV testing & counselling
- ART adherence counselling (HIV+ AGYW)
- STI services information
- Family planning, including counselling, initiation of contraception, services related to current contraception, and pregnancy testing and counselling.
- Information on cervical cancer screening
- Referrals for services, such as mental health, gender-based violence, STI testing, cervical cancer screening, and other health services as needed

All services will be provided based on the standard of care guidelines and delivered by a trained nurse. IWC components and data collection was tested during the pilot-testing phase. In addition, selected staff at the health centers with the IWC clinic will receive stigma training to ensure team-based care is available for AGYW who are referred from the IWC clinic to received services in other departments at the health center. The training section includes four modules (2-hour session for each) that experienced trainers will deliver to give staff the skills to create a stigma-free health facility.^{29,30}

Caregiver and provider support for AGYW. We will include caregivers who will participate with AGYW in the SHIELD family sessions. We will identify one caregiver for each participating AGYW in the 6

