intervention communities (approximately 1,125 family members). The AGYW will select their caregiver upon enrollment into the intervention. We will also include approximately 60 clinic staff in health centers from the 6 communities included in the study. We plan to conduct interviews with these health center staff to seek general feedback on barriers and facilitators faced by youth receiving services at their health centers. We will include health center staff who have worked at the health center for at least 6 months, plan to stay in their current position during the 12-month study implementation period and have some interaction with girls and young women who visit the health center. The staff members at health centers hosting the IWC clinic will receive stigma training at baseline. The staff at each health center will be selected based on their likelihood to interact with AGYW seeking care at their facilities.

Peer navigators support for AGYW. We selected individuals 18 to 24 years to serve as peer navigators to support AGYW enrolled in the study intervention communities/clinics. These navigators were trained to deliver the SHIELD education sessions and they also supported the AGYW during IWC clinic visits.

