
Obtain feedback on the integrated care delivery model and compare with current standard of care. Clinic staff and peer navigator data collection. Two complementary data collection approaches,

IDIs (qualitative) and survey (quantitative; **see Exhibit 2**), will be used to obtain data from about 10 health center staff (clinical and non-clinical) at each of the six health center sites to assess the impact of IWC on HIV care processes, AGYW health seeking behavior, and provider attitudes: The study team will develop an interview guide with key questions to explore staff experiences in providing care to AGYW and their perception about AGYW's satisfaction with the services provided. The study team will include a specific session for the IWC clinic health center staff on implementation procedures, clinic operations, and sustainability. This qualitative information will be supplemented by a survey that will be based on a validated instrument by Co-I [name] for measuring attitudes of providers towards those seeking HIV services (multiple statements that providers can agree or disagree with). This instrument will be adapted for this study and incorporate lessons from an ongoing RTI study in South Africa that is currently adapting the same instrument for vulnerable AGYW (1R01HD094629-01). Additionally, we will also collect details on the implementation climate using a short, tailored questionnaire. These data will be collected at baseline and at 6- and 12-month follow-up to provide a longitudinal assessment of potential changes in provider attitudes.

Furthermore, to assess the implementation of the interventions, we will conduct debrief activities to understand barriers and facilitators experienced by AGYW using surveys, interviews and group discussions with the study team members implementing the interventions. These activities will involve the PNs and the IWC clinic staff who will be working with the AGYW. Furthermore, to understand the level of effort required to implement the interventions and to estimate the cost, we will track time spent by the PNs, IWC clinic staff and others in implementing the SHIELD and IWC clinic interventions.

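### The cost-effectiveness analysis names an IWC-without-SHIELD strategy that no zone receives and leaves out the randomised SHIELD-only arm

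*Combined protocol and SAP*

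**What the plan says.** The Research Protocol part of section 3.3 randomises six zones to three groups: "zones with IWC clinics and SHIELD intervention, zones with only SHIELD intervention, and control zones with no IWC clinic or SHIELD interventions". It gives the middle group its own question, to "evaluate whether a similar impact can be achieved with control clinics when the SHIELD intervention is offered in the community".

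Section 3.2 agrees on the layout. On SHIELD: "The SHIELD sessions will be offered to AGYW and their families in the 4 communities randomly assigned to intervention arms". On the IWC clinic: it "will be established in 2 randomly selected health centers participating in this study communities".

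The cost-effectiveness paragraph of section 3.3 sets out other strategies. Usual care is the base case and is to be "compared to the long-term effectiveness of including the IWC clinic-based intervention with and without the SHIELD community-based interventions". The same paragraph takes the program perspective, feeds the costs and effects of both interventions into existing models, and plans to "perform sensitivity analysis, varying the range of effectiveness and cost estimates".

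**The concern.** Read as written, the economic analysis compares usual care, IWC with SHIELD, and IWC without SHIELD. Two things follow.

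1. IWC without SHIELD was not randomised. Its effect can be had only by assuming how the two components combine, and the plan states neither that assumption nor an outside source for the effect.
2. SHIELD only was randomised, and its costs and effects are to be collected, yet it is not listed as a comparator. What an IWC clinic adds to SHIELD, and at what cost, is therefore not specified.

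The paragraph's perspective reflects the Ministry of Health resources needed to sustain the interventions, and section 3.3.5 takes the modelling results to a government policy forum. As listed, the strategies would give that audience one result resting on an unstated assumption and would omit an increment that randomisation supports directly.

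**Working it through.** **Arms against strategies.** With 6 zones, SHIELD in 4 and IWC in 2, and every IWC zone also a SHIELD zone, there are 4 − 2 = 2 SHIELD-only zones and 6 − 4 = 2 control zones. The sample sizes in section 3.3 also fit three arms and no more: 3 × 200 = 600 HIV-negative or status-unknown participants and 3 × 175 = 525 HIV-positive participants, the stated totals.

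| Strategy | Randomised arm? | In the cost-effectiveness sentence? |
|---|---|---|
| Usual care (control) | yes | yes |
| SHIELD only | yes | no |
| IWC + SHIELD | yes | yes |
| IWC only | no | yes |

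**What three arms identify.** Let b be the control level, i the effect of IWC without SHIELD, s the effect of SHIELD without IWC, and g the IWC-by-SHIELD interaction. The arm means are:

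- control = b
- SHIELD only = b + s
- IWC + SHIELD = b + i + s + g

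With columns (b, i, s, g) the rows are [1,0,0,0], [1,0,1,0] and [1,1,1,1]. The rank is 3 for 4 parameters. A contrast is estimable if adding it as a row leaves the rank at 3.

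| Contrast | Vector | Estimable? |
|---|---|---|
| SHIELD only vs control | [0,0,1,0] | yes |
| IWC + SHIELD vs control | [0,1,1,1] | yes |
| IWC + SHIELD vs SHIELD only | [0,1,0,1] | yes |
| IWC only vs control | [0,1,0,0] | no |
| Interaction | [0,0,0,1] | no |

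**Size.** Let d be IWC + SHIELD minus SHIELD only. Then d = i + g, so i = d − g. If g is set to zero, i = d and becomes estimable. Otherwise, moving g from −5 to +5 points moves i from d + 5 to d − 5, whatever d is. Against the 15-point improvement that the sample-size text of section 3.3 treats as the minimum for success, 5/15 = 33%. The 5-point step is an assumption chosen for scale.

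**Is zero interaction a safe default?** The plan gives reason to doubt it. SHIELD's core topics in Exhibit 1 include where to obtain services, and in IWC zones the peer navigators also link clinic and community. Section 3.2 says they were "trained to deliver the SHIELD education sessions and they also supported the AGYW during IWC clinic visits".

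**Could other planned data help?** SHIELD dose is a planned covariate in section 3.3, but attendance is not randomised, so it gives only observational evidence. On cost, section 3.3 says "we will track time spent by the PNs, IWC clinic staff and others in implementing the SHIELD and IWC clinic interventions". That gives IWC costs as a component, but only in zones where SHIELD also runs.

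**The case against.** The strongest case against has five parts.

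- **It may be a slip of wording.** If SHIELD with and without IWC was meant, every comparison is estimable and the interaction argument falls away. This is plausible, but nothing in the documents confirms it, and the sentence needs correcting on either reading.
- **A decision model may include strategies that were not trialled.** True. The plan would then need to say how the IWC-only effect is derived. It refers to previously validated models, and those may contain a rule for combining components, but none is stated here.
- **The sensitivity analysis could cover it.** It varies effectiveness and cost, with best and worst cases. It does not name the interaction, and no randomised data constrain a range for it.
- **Costs can be separated.** Staff time is tracked by activity, and SHIELD-only zones show navigator time without an IWC clinic. This largely stands: the cost side is the weaker part of the concern, and the effect side carries it.
- **The arms are not perfectly clean.** Controls receive one education session drawn from SHIELD topics, and the increment of IWC over SHIELD rests on two zones per arm. Both are fair cautions. Section 3.2 itself calls the control group the usual care arm, so the restated strategies still match the arms, and a contrast estimated from four zones remains better founded than one with no arm.

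**Conclusion.** The concern holds. The listed economic strategies do not match the randomised arms: one has no arm and one arm is missing. On the literal reading, the IWC-alone effect is not identified without an interaction assumption, and it shifts point for point with whatever value is assumed. On the reversed reading, the fault is confined to wording and all comparisons are identified.

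The mismatch itself is certain from the text. The numerical consequence applies only to the literal reading, and its 5-point scale is illustrative. The effect is limited to Objective 3: the primary endpoints, randomisation, sample size and data collection are untouched. It should be corrected before the economic analysis is reported.

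**What to change.** Rewrite the sentence in the cost-effectiveness paragraph of section 3.3 so that the strategies are usual care as base case, SHIELD without an IWC clinic, and SHIELD with an IWC clinic, with incremental cost-effectiveness ratios between successive strategies. It would help to note that the control arm received one education session.

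If IWC alone is still of policy interest, present it as a modelled scenario and label it so. State the interaction assumption and vary it in the sensitivity analysis already planned.

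The cost is one sentence, plus a line for the scenario if it is kept. Costs and effects for both SHIELD strategies are already to be collected, so no new data are needed.
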